3. We aim to describe the prevalence of common mental health conditions (anxiety, depressive episodes, and recurrent depressive disorder) in people with IBD when compared to an age and gender matched cohort.
4. We aim to explore healthcare utilisation in individuals with IBD with and without common mental health problems.

Methods

Study design

We aim to perform a retrospective matched cohort study. We will match people with UC and CD, to people without IBD. A history of common mental health conditions was assessed at baseline (matching date) in both cohorts, and compared. Both cohorts will be followed-up (retrospectively) from the matching date for incident infections, and healthcare resource utilisation.

Data source

We aim to use the Royal College of General Practitioners (RCGP) Research and Surveillance Centre (RSC) database. This database contains the pseudonymised primary care records of the registered population all from a network of GP practices which provide a representative sample of the UK population.⁹ The RCGP RSC database contains complete data on all events and clinical entities coded in UK primary care. These include demographic information, clinical diagnoses, laboratory test results, primary care issued prescriptions, process of care codes (e.g. specialist referrals), and anthropometric measurements (e.g., body mass index; BMI), and are coded using the Read coding system.¹⁰

UK general practice records provide several advantages for this study type;^{11, 12} UK primary care is a registration-based system (a patient can only register with a single GP), records have been computerised since the 1990s, and pay-for-performance targets (introduced in 2004 through The Quality and Outcomes Framework; QOF) have resulted in consistent high-quality clinical data entry about chronic disease. Studies using the RCGP RSC data have been published across a range of chronic diseases.¹³⁻¹⁵ RCGP RSC practices get feedback on their data quality, including using a dashboard. A particular emphasis of this feedback is “episode typing” – designating cases first, new, or ongoing – which helps differentiate incidence from prevalence.¹⁶

Study population and outcome measures

All adults (aged ≥ 18) registered with a GP practice contributing to the RCGP RCS at the time of data extraction will be eligible for inclusion.

Definition of the IBD cohort

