The presence of common mental health conditions at baseline will be determined for the case and control cohorts. We will examine three groups of common mental illness as defined by the International Statistical Classification of Diseases and Related Health Problems 10th Revision (ICD10) classification;²⁰ depressive episodes (F32), recurrent depressive disorder (F33), and non-phobia related anxiety disorders (F41). These conditions are chosen as they represent the most common mental health conditions presenting to primary care.²¹ These conditions will be identified using algorithms validated in UK primary care.²² We selected the algorithms used here (Appendix 2) to optimise the positive predictive value. In brief, we will use a concurrent diagnosis and treatment code to identify acute episodes (depressive episodes and anxiety episodes) and for recurrent depression either a historical code for any depression and current treatment or a recurrent

depression specific diagnosis code (Appendix 2). As a secondary analysis we will also explore the prevalence of attention deficit hyperactivity disorder (ADHD) in the case and control cohorts.

Healthcare utilisation outcomes

The components of healthcare utilisation to be examined comprise; number and duration of primary care attendances, number of primary care prescriptions for antidepressant and anxiolytic medications, number of primary care prescriptions for medications used in IBD, recorded secondary care attendances, and issue of statements of fitness for work (also termed fit notes or sick notes).

Antidepressant medication classes to be examined comprise, selective serotonin reuptake inhibitors (SSRIs) and related medications (serotonin and norepinephrine reuptake inhibitors; SNRIs), tricyclic antidepressants (TCAs) and related medications (tetracyclic antidepressant TeCAs), and monoamine oxidase inhibitors (MOAIs). Anxiolytic medications to be examined comprise all benzodiazepines and other related medications indicated for use in anxiety states (Appendix 3). Medications used for the treatment of IBD to be examined will comprise; topical 5-aminosalicylic acid (5-ASA) medications, topical glucocorticoids, oral 5-ASA medications, oral glucocorticoids, non-biologic immunosuppressant medications (cyclosporine, azathioprine, mercaptopurine, methotrexate), and biologic therapies (Appendix 3).

Other baseline measures

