Socioeconomic status will be defined using the official national measure; the index of multiple deprivation (IMD).²³ This is calculated at the point of data extraction, using patient postcode, with the resultant scores stratified by deprivation quintile. Ethnicity will be extracted from the primary care record and grouped into major ethnic groups; white, black, Asian, mixed, and others.²⁴ BMI will be defined as the most recently recorded measurement prior to the study start date. Smoking status will be defined using the most recently recorded data prior to the study start date. Diagnosis codes will be used to define the presence of comorbidities at baseline; diabetes, hypertension, atrial fibrillation, angina, myocardial infarction, congestive heart failure, stroke, transient ischaemic attack, chronic kidney disease (stages 3–5), dementia, rheumatoid arthritis, chronic liver disease, asthma and chronic obstructive pulmonary disease (COPD).

Statistical Analyses

Comparison of the prevalence of mental health conditions

We will compare the prevalence of the three common mental health conditions in people with IBD and matched controls prior to the baseline date (January 1, 2015). We will stratify groups by age, and gender, and for those with IBD by condition (UC or CD) and duration of disease, and other important baseline factors. We will evaluate differences in baseline characteristics between the cohorts using the χ^2 test for categorical variables and the unpaired t-test for continuous data. Other statistical tests may be used if appropriate, depending on the data type and distribution.

Comparison of healthcare utilisation

We will compare the measures of healthcare utilisation between people with IBD and matched cohorts over a follow-up period. Follow-up will end at the earliest of; the study end-date (data extraction date), the date of patient transfer from an included practice, or date of death. All individuals contributing at least 1 day of follow-up will be included for analysis. We will stratify and compare healthcare utilisation in people with IBD by age and gender, condition (UC or CD), duration of disease, the presence of mental health conditions, and other important

confounders. All utilisation outcomes will be adjusted for the duration of follow-up and reported as event rates.

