XaK6C	All	Exacerbation of Crohn's disease of small intestine
J400z	All	Crohn's disease of the small bowel NOS
J401.	All	Regional enteritis of the large bowel
XE0af	All	Crohn's disease of the large bowel NOS
XaK6D	All	Exacerbation of Crohn's disease of large intestine
J40z.	All	Regional enteritis NOS
J4010	All	Crohn's colitis
J4011	All	Crohn's proctitis
X3050	All	Perianal Crohn's disease
Jyu40	All	[X]Other Crohn's disease

Supplementary table S1. Read codes used to identify inflammatory bowel disease

Appendix 2

Clinical entity	ICD 10 code	Definition
Anxiety	F41	Any coded anxiety episode AND concurrent treatment for anxiety
Depressive episode	F32	Any coded depressive episode AND concurrent treatment for depression
Recurrent depressive disorder	F33	(Any historical code* for a depressive episode AND current treatment for depression) OR Any code for recurrent depressive disorder
Anxiety treatments	NA	SSRIs, anxiolytics, counselling, CBT, and psychotherapy
Depression treatments	NA	SSRIs, TCAs, MAOIs, counselling, CBT, and psychotherapy

Supplementary table S2. Algorithms used to identify anxiety episodes, depression episodes, and recurrent major depression. Expressions in capitals equate to Boolean expressions. *More than 1 year ago. SSRIs = selective serotonin reuptake inhibitors, TCA = tricyclic antidepressants, MAOI = monoamine oxidase inhibitors, CBT = cognitive behavioural therapy.

Read V2 Code	Term ID	Description
E200.	All	Anxiety states
E2000	All	Anxiety state unspecified
E2001	All	Panic disorder
E2002	All	Generalised anxiety disorder
E2003	All	Anxiety with depression
E2004	All	Chronic anxiety
E2005	All	Recurrent anxiety
E200z	All	Anxiety state NOS
Eu41.	All	[X]Other anxiety disorders
Eu410	All	[X]Panic disorder [episodic paroxysmal anxiety]
Eu411	All	[X]Generalized anxiety disorder
Eu412	All	[X]Mixed anxiety and depressive disorder
Eu413	All	[X]Other mixed anxiety disorders
Eu41y	All	[X]Other specified anxiety disorders
Eu41z	All	[X]Anxiety disorder, unspecified
Read CTV3 Code	Term ID	Description
E200.	All	Anxiety disorder
XE1Y7	All	Panic disorder
Eu410	All	[X]Panic disorder [episodic paroxysmal anxiety]
E2002	All	Generalised anxiety disorder
X00Sb	All	Mixed anxiety and depressive disorder
X00RP	All	Organic anxiety disorder
E2004	All	Chronic anxiety
E2005	All	Recurrent anxiety
E200z	All	Anxiety state NOS
X00Sc	All	Anxiety hysteria
Eu41.	All	[X]Other anxiety disorders
Eu413	All	[X]Other mixed anxiety disorders

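### Aim 4 compares antidepressant and anxiolytic prescription rates by a mental-health status that itself depends partly on treatment with those drugs, which biases the contrast upward

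*Combined protocol and SAP*

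**What the plan says.** **Exposure.** Appendix 2, Supplementary table S2, defines anxiety as "Any coded anxiety episode AND concurrent treatment for anxiety" and depressive episode as "Any coded depressive episode AND concurrent treatment for depression". Recurrent depressive disorder has two routes. One is "Any historical code* for a depressive episode AND current treatment for depression", where historical means more than one year ago. The other is any recurrent-depression code (listed in S5), with no treatment needed. Qualifying treatments are SSRIs, anxiolytics or talking therapy for anxiety, and SSRIs, TCAs, MAOIs or talking therapy for depression. The Mental health outcomes section says these algorithms were chosen for their positive predictive value.

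**Outcome.** The Healthcare utilisation outcomes section includes the "number of primary care prescriptions for antidepressant and anxiolytic medications". Appendix 3 (S7) gives one drug list by class. S2 names the same classes and has no list of its own.

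**Comparison.** Aim 4 reads: "We aim to explore healthcare utilisation in individuals with IBD with and without common mental health problems". The Comparison of healthcare utilisation section stratifies and compares utilisation in IBD by several factors, including "the presence of mental health conditions". It reports all utilisation outcomes as event rates and exempts none from this comparison.

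**Timing.** Mental-health status is determined at baseline (1 January 2015). Utilisation is counted from the matching date onward.

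**The concern.** The same drug classes appear on both sides of one Aim 4 contrast: as a means of entering the 'with' group, and as the outcome. Antidepressant and anxiolytic treatment often runs on, so a group chosen partly for being on treatment starts follow-up with a higher expected prescription count, whatever the condition itself does to resource use.

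The 'without' group is affected too. A person with an anxiety or depressive-episode code but no qualifying treatment is placed there unless a recurrent-depression code applies. The label 'without' therefore covers some diagnosed people in every Aim 4 utilisation contrast, although only the prescription contrast has the drug overlap.

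What is at stake is interpretation. The Lay Summary describes the work as showing the impact of mental health problems on healthcare use, names medication prescriptions among the components, and links the results to resource allocation. Read that way, an excess that partly restates the definition would be reported as a resource-use finding.

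**Working it through.** The documents give no sample size, expected prescription rate or code prevalence for Aim 4, so there is no planned figure to reproduce. Every value below is an assumption, chosen to show how the bias behaves.

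**Null model.** A diagnosis code carries no information about drug treatment, talking therapy or later prescribing, and drug and talking therapy are independent. Status is a code plus at least one of the two treatments.

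- c = share with a diagnosis code: 10-30%
- d = share on a relevant drug: 10-20%
- t = share with talking therapy: 2-10%
- k = later prescription rate in people on drug when classified, divided by the rate in people not on drug: 1, 2, 5, 10

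**Formulas.**

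- Share treated: T = 1 − (1 − d)(1 − t)
- Share on drug in the 'with' group: p1 = d / T
- Share on drug in the 'without' group: p0 = d(1 − c) / (1 − cT)
- Rate ratio: RR = [1 + p1(k − 1)] / [1 + p0(k − 1)]

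**Worked case** (c = 0.20, d = 0.15, t = 0.05, k = 5).

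- T = 1 − 0.85 × 0.95 = 0.1925
- p1 = 0.15 / 0.1925 = 0.779
- p0 = 0.15 × 0.80 / (1 − 0.20 × 0.1925) = 0.12 / 0.9615 = 0.125
- RR = (1 + 0.779 × 4) / (1 + 0.125 × 4) = 4.117 / 1.499 = 2.75

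**Range over the corner values of c, d and t.**

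| k | Lowest RR | Highest RR |
|---|---|---|
| 1 (no carry-over) | 1.00 | 1.00 |
| 2 | 1.40 | 1.72 |
| 5 | 2.22 | 3.40 |
| 10 | 2.79 | 5.22 |

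The highest values come from c = 0.30, d = 0.10, t = 0.02. There T = 0.118, p1 = 0.847 and p0 = 0.07 / 0.9646 = 0.0726. At k = 10, RR = 8.627 / 1.653 = 5.22.

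**Effect of the code-only route.** Suppose a share q of the 'with' group qualifies by a recurrent-depression code alone, so that its chance of being on drug is d. In the worked case with q = 0.5, the share on drug is 0.5 × 0.779 + 0.5 × 0.15 = 0.465. Then RR = (1 + 0.465 × 4) / 1.499 = 1.91, against 2.75. This holds p0 at its earlier value, which is a simplification.

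**Code-only status.** If status is the code regardless of treatment, both groups have share d on drug under this null. Then p1 = p0 and RR = 1.00 at every k.

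**The case against.** A reader might infer that the contrast is positive by construction and cannot come out null. The documents do not support that, for five reasons:

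- A diagnosis code is always required; treatment alone never confers status.
- Recurrent depressive disorder can qualify by code alone, and S5 includes chronic-depression and remission codes.
- Talking therapy alone qualifies, and it is not part of the prescription count.
- Treated people without a code stay in the 'without' group. So can an anxiety-coded person taking only a TCA, or a person with a depressive-episode code taking only an anxiolytic, because S2 does not count those pairings.
- Status is fixed at baseline and counting starts there, so no prescription is used twice. For anxiety and depressive episode the treatment must be concurrent with a coded episode, and that episode may be old.

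All of this stands. It makes the bias depend on carry-over, with no bias under the null model at k = 1. It does not remove the bias, because the plan sets no window for 'concurrent' or 'current' and so does not limit carry-over.

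It is also fair that Aim 4 is exploratory, that prescribing volume in treated patients is a legitimate descriptive quantity, and that the algorithms were a deliberate choice. That is a reason to keep the outcome and label it, rather than delete it. Positive predictive value is a good reason to use S2 for prevalence, but it does not answer the overlap when the same status serves as an exposure for prescribing.

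**Conclusion.** The concern holds in a limited form. Following the plan as written gives an Aim 4 contrast in antidepressant and anxiolytic prescription rates that is biased upward to the extent that treatment at classification continues into follow-up. The plan neither acknowledges the overlap nor includes a code-only analysis.

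The size cannot be fixed from the documents. Under the assumed ranges and a null in which the code is uninformative, the spurious rate ratio runs from 1.00 with no carry-over to 5.22 at tenfold carry-over. A substantial code-only share pulls it down. These figures illustrate the mechanism and do not forecast the study's result.

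The other utilisation outcomes do not share the drug overlap. For them the issue is that some coded but untreated people are labelled 'without', and the size of that effect is not quantified here. The IBD versus matched-control comparison of prescriptions is unaffected by this point.

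**What to change.** - Keep S2 for the prevalence comparison in Aim 3, and keep prescription counts for IBD versus matched controls.
- For Aim 4, repeat the with/without comparison for every utilisation outcome, including antidepressant and anxiolytic prescriptions, with status defined by diagnosis code regardless of treatment, using the lists in S3-S5.
- Report the prescription contrast under the S2 definition as descriptive only, and state that the definition and the outcome share drug classes.
- State the window meant by 'concurrent' and 'current', so that a reader can judge the likely carry-over.

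This is a cheap improvement: a few sentences of protocol text and one re-run with code lists that already exist. The downside is that a code-only definition has lower positive predictive value, which is why it is proposed alongside S2 and not in its place.

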Eu41z	All	[X]Anxiety disorder, unspecified
XE1Zj	All	[X]Other specified anxiety disorders

Supplementary table S3. Read codes used to identify anxiety episodes.

Read V2 Code	Term ID	Description
E0013	All	Presenile dementia with depression
E0021	All	Senile dementia with depression
E112.	All	Single major depressive episode
E1120	All	Single major depressive episode, unspecified
E1121	All	Single major depressive episode, mild
E1122	All	Single major depressive episode, moderate
E1123	All	Single major depressive episode, severe, without mention of psychosis
E1124	All	Single major depressive episode, severe, with psychosis
E1125	All	Single major depressive episode, in partial or unspecified remission
E1126	All	Single major depressive episode, in full remission
E112z	All	Single major depressive episode NOS
E113.	All	Recurrent major depressive episode
E1130	All	Recurrent major depressive episodes, unspecified
E1131	All	Recurrent major depressive episodes, mild
E1132	All	Recurrent major depressive episodes, moderate
E1133	All	Recurrent major depressive episodes, severe, without mention of psychosis
E1134	All	Recurrent major depressive episodes, severe, with psychosis
E1137	All	Recurrent depression
E113z	All	Recurrent major depressive episode NOS
E118.	All	Seasonal affective disorder
E11y2	All	Atypical depressive disorder
E11z2	All	Masked depression
E130.	All	Reactive depressive psychosis
E135.	All	Agitated depression
E2003	All	Anxiety with depression
E291.	All	Prolonged depressive reaction
E2B..	All	Depressive disorder NEC
E2B1.	All	Chronic depression
E2B0.	All	Postviral depression
Eu204	All	[X]Post-schizophrenic depression
Eu251	All	[X]Schizoaffective disorder, depressive type
Eu32.	All	[X]Depressive episode
Eu320	All	[X]Mild depressive episode
Eu321	All	[X]Moderate depressive episode
Eu322	All	[X]Severe depressive episode without psychotic symptoms
Eu323	All	[X]Severe depressive episode with psychotic symptoms
Eu324	All	[X]Mild depression
Eu325	All	[X]Major depression, mild
Eu326	All	[X]Major depression, moderately severe
Eu327	All	[X]Major depression, severe without psychotic symptoms
Eu328	All	[X]Major depression, severe with psychotic symptoms

Eu32y	All	[X]Other depressive episodes
Eu32z	All	[X]Depressive episode, unspecified
Eu33.	All	[X]Recurrent depressive disorder
Eu330	All	[X]Recurrent depressive disorder, current episode mild
Eu331	All	[X]Recurrent depressive disorder, current episode moderate

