Eu332	All	[X]Recurrent depressive disorder, current episode severe without psychotic symptoms
Eu333	All	[X]Recurrent depressive disorder, current episode severe with psychotic symptoms
Eu334	All	[X]Recurrent depressive disorder, currently in remission
Eu33y	All	[X]Other recurrent depressive disorders
Eu33z	All	[X]Recurrent depressive disorder, unspecified
Eu412	All	[X]Mixed anxiety and depressive disorder
Read CTV3 Code	Term ID	Description
X00Sb	All	Mixed anxiety and depressive disorder
X00SO	All	Depressive disorder
X761L	All	Seasonal affective disorder
Xa0wV	All	Recurrent brief depressive disorder
X00SQ	All	Agitated depression
XE1YC	All	Reactive depression
X00SR	All	Endogenous depression
X00SS	All	Endogenous depression first episode
XE1Y0	All	Single major depressive episode
E1120	All	Single major depressive episode, unspecified
E1120	All	Single major depressive episode, unspecified
E1121	All	Single major depressive episode, mild
E1122	All	Single major depressive episode, moderate
E1123	All	Single major depressive episode, severe, without mention of psychosis
E1124	All	Single major depressive episode, severe, with psychosis
XaX53	All	Single major depressive episode, severe, with psychosis, psychosis in remission
E1125	All	Single major depressive episode, in partial or unspecified remission
E1126	All	Single major depressive episode, in full remission
E112z	All	Single major depressive episode NOS
XM1GC	All	Endogenous depression - recurrent
E1130	All	Recurrent major depressive episodes, unspecified
E1131	All	Recurrent major depressive episodes, mild
E1132	All	Recurrent major depressive episodes, moderate
E1133	All	Recurrent major depressive episodes, severe, without mention of psychosis
E1134	All	Recurrent major depressive episodes, severe, with psychosis
E1135	All	Recurrent major depressive episodes, in partial or unspecified remission
E1136	All	Recurrent major depressive episodes, in full remission
E113z	All	Recurrent major depressive episode NOS

X00SU	All	Masked depression
E11y2	All	Atypical depressive disorder
X00S8	All	Post-schizophrenic depression
XSEGJ	All	Major depressive disorder
XSKr7	All	Cotard syndrome
XSGol	All	Moderate major depression
XSGok	All	Mild major depression
XSGom	All	Severe major depression without psychotic features
XSGon	All	Severe major depression with psychotic features
E1137	All	Recurrent depression
E130.	All	Reactive depressive psychosis
E2B..	All	Depressive disorder NEC
E2B0.	All	Postviral depression

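### The depressive-episode (F32) code list includes mixed anxiety-depression codes that also define anxiety (F41), plus schizophrenia-spectrum codes, so the two endpoints partly overlap and F32 prevalence is biased upward

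*Combined protocol and SAP*

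**What the plan says.** The Mental health outcomes section names three ICD-10 groups: "depressive episodes (F32), recurrent depressive disorder (F33), and non-phobia related anxiety disorders (F41"). It says the algorithms were selected "to optimise the positive predictive value". It also says that "we will use a concurrent diagnosis and treatment code to identify acute episodes (depressive episodes and anxiety episodes").

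Appendix 2, table S2 gives the rules. Anxiety is "Any coded anxiety episode AND concurrent treatment for anxiety". Depressive episode has the same form, with a depression code and a depression treatment. Recurrent disorder needs either a depressive-episode code more than a year old with current treatment, or a recurrent-specific code. SSRIs, counselling, CBT and psychotherapy are on both treatment lists. Anxiolytics are on the anxiety list only, and TCAs and MAOIs on the depression list only.

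Table S3 lists the anxiety codes and table S4 the depressive-episode codes. Eu412, "X]Mixed anxiety and depressive disorder", is in both. S4 also includes Eu251, "X]Schizoaffective disorder, depressive type", and E1126, "Single major depressive episode, in full remission".

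The plan does not say whether the three groups may overlap. It gives no rule allocating a mixed code to one group, and no sensitivity analysis on the code lists.

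**The concern.** Aim 3 asks for the prevalence of anxiety and of depressive episodes in IBD against matched controls, as distinct conditions. If one diagnostic code can satisfy both definitions, part of the depression estimate is made up of patients whom the plan's own classification places under anxiety. Codes for schizophrenia-spectrum illness add people who belong to neither group. Both work against the stated aim of a high positive predictive value.

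Two results are exposed. The absolute F32 prevalence is raised. The IBD-versus-control ratio for F32 becomes a blend of the ratio for depressive episodes and the ratio for the added conditions. Aim 4 is affected too, because healthcare utilisation is to be stratified by the presence of mental health conditions.

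**Working it through.** **No figure to reproduce.** The documents give no expected prevalence, code frequency or sample size for these endpoints. For baseline differences they name only the "χ^2 test for categorical variables and the unpaired t-test for continuous data". The check is therefore a comparison of the lists, followed by arithmetic on stated assumptions.

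**Step 1: compare the lists (Appendix 2, S3 and S4).**

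| | Read V2 | CTV3 |
|---|---|---|
| Codes in S3 | 15 | 14 |
| Distinct codes in S4 | 52 | 60 (61 rows; E1120 twice) |
| In both S3 and S4 | E2003, Eu412 | X00Sb |
| Schizophrenia-spectrum in S4 | Eu204, Eu251 | X00S8 |
| Dementia with depression in S4 | E0013, E0021 | E0013, E0021 |
| In-remission codes in S4 | E1125, E1126, Eu334 | E1125, E1126, E1135, E1136, XaX53 |

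Shared entries: 2 + 1 = 3 of 15 + 14 = 29 in S3.

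**Step 2: where the codes belong on the plan's own grouping.** The Eu numbering follows the ICD-10 groups: Eu32 is depressive episode, Eu33 recurrent depressive disorder, Eu41 other anxiety disorders. Eu412 therefore falls in the anxiety block. E2003 likewise sits under E200, which S3 lists as anxiety states. X00Sb has no such numbering, and its placement rests on having the same label as Eu412. Eu204 and Eu251 lie outside Eu32, and their labels name schizophrenia-spectrum conditions. X00S8 carries the same label as Eu204.

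**Step 3: follow one patient through S2.**
- Eu412 with an SSRI: anxiety yes, depressive episode yes.
- Eu412 with an anxiolytic only: anxiety only.
- Eu412 with a TCA or MAOI only: depressive episode only. Clomipramine is the exception, because S7 lists it under both TCAs and anxiolytics.

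**Step 4: size of the excess in F32 prevalence (assumed range).** Let s be the share of F32-positive patients who qualify only through the six codes. Relative excess = s/(1 − s).

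| s | 1% | 5% | 10% | 20% | 30% |
|---|---|---|---|---|---|
| Excess | 1.0% | 5.3% | 11.1% | 25% | 42.9% |

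**Step 5: effect on the cohort ratio (assumed values).** Let d be the control prevalence of F32 without the contested codes, m the control prevalence qualifying only through them, and R_d and R_m the IBD-to-control ratios for each part. Reported ratio = (R_d·d + R_m·m)/(d + m). Take d = 8%.
- R_d = 1.0, R_m = 1.5, m = 2%, 3%, 4%: 11/10 = 1.10; 12.5/11 = 1.14; 14/12 = 1.17, where the depressive-episode ratio is 1.00.
- R_d = 1.25, R_m = 1.0, m = 2%: 12/10 = 1.20, where the depressive-episode ratio is 1.25.
- R_d = R_m = 1.25, m = 2%: 12.5/10 = 1.25, no change.

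The ratio can move up, down or not at all.

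**The case against.** **Overlap may be intended.** The plan never claims exclusive groups, and someone recorded as having anxiety with depression can reasonably count under both. A reader might infer that the two endpoints cannot be separated. The documents do not support that: 26 of 29 S3 entries are not in S4, and the treatment condition separates some patients with a mixed code. What stands against the plan is narrower. A single code, not two diagnoses, produces both positives, and no rule says so.

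**The algorithms are described as validated in UK primary care.** True, and the documents do not show whether the validated lists contained these codes. Removing them may depart from the validated definition. This is a reason to keep the pooled version as a sensitivity analysis, not to leave F32 at odds with its stated grouping.

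**The same lists apply to both cohorts.** This protects the ratio only if the contested codes carry the same IBD-to-control ratio as the rest of F32 (Step 5). It does not protect the absolute prevalence.

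**Remission and dementia codes.** A reader might infer that the remission codes are plain misclassification, because the rule is said to find acute episodes. That goes too far. The Study design section speaks of a history of these conditions at baseline, and a treated single-episode code in remission is evidence that an episode occurred. The dementia codes name depression in their labels. Both are judgement calls.

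**Conclusion.** The concern holds in a limited form. Six S4 codes (Eu412, E2003, X00Sb, Eu204, Eu251, X00S8) do not fit F32 as the plan groups its endpoints. Three of them also define anxiety, so F32 and F41 partly overlap. The direction for absolute F32 prevalence is upward compared with the same list without these codes, because extra codes in an any-code list can add cases but not remove them.

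The size is unknown. A reader might take 20% to 33% of F32 cases as misplaced, from 2/(8 + 2) and 4/(8 + 4). Those figures need assumed prevalences of 8% for depression-only and 2% to 4% for mixed codes. They also assume that every mixed-code patient meets the treatment condition and carries no other S4 code. The documents support none of this. Nor do they show that the IBD comparison is biased, which would need the contested codes to be distributed differently between cohorts from the rest of F32.

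The point merits a change before analysis: the mismatch is with the plan's own definition, and the remedy needs no new data.

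**What to change.** 1. Remove Eu204, Eu251 and X00S8 from S4.
2. Report E2003, Eu412 and X00Sb as a separate mixed anxiety and depression row. In the main analysis count them under F41 and not F32. S4 then falls from 52 to 48 V2 codes and from 60 to 58 distinct CTV3 codes, and shares none with S3.
3. Add an any-anxiety-or-depression total with each patient counted once. For this total and the mixed row, accept treatment from either list. Otherwise a mixed code treated only with a TCA or MAOI would drop out of every row.
4. Sensitivity analysis A: restore the mixed codes to F32, for comparability with the cited algorithm.
5. Sensitivity analysis B: drop the dementia codes (E0013, E0021) and all in-remission codes (E1125, E1126, Eu334, CTV3 E1135 and E1136, XaX53), consistently in both Read versions.
6. State that patients with separate codes may count in more than one group, and whether the first limb of the recurrent rule uses the edited S4.

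Do not recast E1125 and E1126 as history only. The only historical-code route in S2 leads to recurrent disorder, so single-episode codes would then count solely towards F33.

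The cost is a code-list edit and a few output rows. The downside is that F32 prevalence falls, and the main estimate may differ from the validated algorithm and from studies that pool mixed codes into depression. The overlap between S4 and the recurrent list S5 (34 of 38 S5 entries) is a separate matter that these steps leave unchanged in the main analysis.
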